Additionally, 80 liver tissue samples from patients with advanced MASLD will be sequenced to identify specific somatic mutations. Expected outcomes of this study include the identification of novel genetic variants associated with MASLD progression, improved risk stratification through the development of polygenic risk scores, and the identification of potential therapeutic targets. This

study represents a fundamental step in understanding the biology of MASLD and could have important clinical implications for disease management.

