### 2.1 Primary objective

The primary objective of this study is to identify genetic variants (germline and/or somatic) associated with the risk of developing advanced MASLD (fibrosis  $\geq 2$  and/or hepatocellular carcinoma) in the Italian population.

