### 2.2 Secondary objectives

The secondary objectives of this study are:

- To characterize the contribution of somatic variants (in hepatocytes and hematopoietic cells) that are involved in the progression of advanced MASLD;
- Evaluate and develop polygenic risk scores (PRS) for risk stratification and identification of specific subphenotypes;
- To study the associations between genetic variants and metabolic phenotypes related to MASLD;
- Identify relevant therapeutic targets for the development of precision medicine strategies in advanced MASLD.

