- Non-Invasive Liver Injury Assessment (Fibroscan): Essential to confirm the absence of significant liver fibrosis in these controls, although they may have steatosis or early NASH.
- OMIC characterization (in a subset): This is a distinctive feature of this cohort, which includes circulating lipidomics, metabolomics, and metagenomics. It provides a very high level of molecular detail on their metabolic profiles and gut microbiome, crucial for understanding gene-environment-metabolism interactions.
- Prospective Follow-up Assessments: The longitudinal nature of the Liver-BIBLE Milano study means that follow-up data will be updated over time, providing information on the evolution of their metabolic and health status.

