#### 4.3 Sample analysis

The genetic analyses for this study will be conducted in close collaboration and under the supervision of Human Technopole.

As anticipated, the methodology envisaged for conducting this study involves whole-genome sequencing on DNA derived from peripheral blood (20x coverage) and pathological liver tissue (50x coverage) to characterize the genetic and somatic variants that influence disease progression.

The DNA will be isolated at the Foundation and shipped to the National Facility (NF) in batches of 3-4 plates at a time.

To identify associations between individual genetic variants and the burden of likely loss-of-function (LoF) variants at specific genetic loci, comparing participants with advanced MASLD to controls, analyses will be performed using a genome-wide regression model implemented in REGENIE, with additive genetic models accounting for age, sex, body mass index (BMI), and ancestry (BWI 1-10). To ensure the robustness of the results, the genome-wide significance threshold will be set at  $p < 5E-8$ . If the study is not powered to identify new significant associations, suggestive hits ( $p < 5E-6$ ) will be replicated in additional cohorts.

In addition to defining the risk of advanced MASLD compared to controls as the primary outcome, we will thoroughly examine the genetic contribution to various endophenotypes. These will include metabolic risk factors (such as insulin resistance indices), liver enzymes (AST, ALT, GGT), and indicators of liver damage (noninvasive predictors of steatosis, steatohepatitis, fibrosis, cirrhosis, and HCC). The results of these analyses will be crucial for improving risk stratification and identifying specific disease subphenotypes through the development of polygenic risk scores, which have previously proven effective in identifying subsets of patients at specific risk for liver or cardiovascular events. This approach will also aim to identify therapeutic targets with a high probability of clinical success.

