## 5. ENDPOINT

### 5.1 Primary Endpoint

Identifying the association between germline variants and the presence of advanced MASLD in cases versus controls.

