## 6. STATISTICAL ANALYSIS

### 6.1 Sample size

The total number of samples for which Whole Genome Sequencing (WGS) is planned is 2,880, including 800 subjects with advanced MASLD, 2,000 controls with at least two characteristic criteria of metabolic syndrome but free of advanced liver disease, and 80 liver tissue samples for somatic variant analysis. The sample size estimate is based on the study's primary objective, which is the identification of genetic variants (germline and/or somatic) associated with MASLD.

The study is descriptive with a power proportional to the number of subjects included.

This number was defined on the basis of the maximum availability of subjects that could be enrolled in the clinical cohorts with the aim of maximizing the statistical power and scientific value of the results. Preliminary data on common variants are available that confirm the statistical power of the cohort to identify phenotype-associated variants at the genome-wide level..

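### The advanced-MASLD versus metabolic-control contrast answers the primary endpoint, but cannot by itself support calling germline findings progression findings

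*Protocol*

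**What the plan says.** **Formal aims.** Protocol 2.1 seeks variants "associated with the risk of developing advanced MASLD", and the primary endpoint (5.1) is "Identifying the association between germline variants and the presence of advanced MASLD in cases versus controls". The one formal objective that names progression (2.2) concerns somatic variants: "To characterize the contribution of somatic variants (in hepatocytes and hematopoietic cells) that are involved in the progression of advanced MASLD".

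**Progression wording that reaches germline variants.** The expected outcomes in 1.1 include "the identification of novel genetic variants associated with MASLD progression". Section 4.3 says that sequencing of blood and liver DNA serves "to characterize the genetic and somatic variants that influence disease progression".

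**Controls.** Section 6.1 describes "2,000 controls with at least two characteristic criteria of metabolic syndrome but free of advanced liver disease". Section 3.2 admits donors on BMI and metabolic factors, with no steatosis criterion. Section 4.2 matches them on sex and metabolic risk factors and says of their Fibroscan assessment: "Essential to confirm the absence of significant liver fibrosis in these controls, although they may have steatosis or early NASH". The steatotic share is not stated.

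**Model.** The REGENIE model in 4.3 adjusts for age, sex, BMI and ancestry, but not steatosis. Separately, 4.3 and secondary endpoint 3 in 5.2 plan germline analyses of liver enzymes, metabolic traits and non-invasive indicators of steatosis and fibrosis. Section 4.3 also lists indicators of steatohepatitis, cirrhosis and HCC. No comparison of advanced with non-advanced disease among steatotic people is named.

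**The concern.** Cases have steatotic liver disease by diagnosis, whereas controls may or may not. A variant that only makes steatosis more likely will therefore be commoner in cases than in the mixed control group, even if it has no effect on the step from steatosis to fibrosis or HCC. Adjusting for BMI does not remove a difference that arises through liver fat.

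The association is real as an association with advanced MASLD. What is at stake is the label. A locus, polygenic score or therapeutic target could be presented as bearing on progression when it reflects only who develops a fatty liver. A score of that kind need not rank risk among patients who already have MASLD. Replicating suggestive hits (4.3) would not resolve this if the replication cohorts had the same mix of controls.

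**Working it through.** **1. Check of the method on the protocol's own figure.** Section 6.1 states power above 95% for OR 2 at allele frequency 0.1, with 800 cases, 2000 controls and significance level 5E-8. Using a two-sided comparison of allele frequencies (1600 case alleles, 4000 control alleles, critical value 5.45), the case frequency is 0.182 and the power is 0.996. A likelihood-ratio version gives 0.974 to 0.996. The figure reproduces.

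**2. Inputs for the present question.**
- From the protocol: 800 cases, 2000 controls, threshold 5E-8, suggestive threshold 5E-6.
- Assumed, because the protocol gives no value: steatotic share of controls s = 30%, 50% or 70%; control allele frequency 0.3; allelic OR on steatosis 1.5, 2.0 or 2.5; no effect on progression; all cases steatotic.

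**3. Formulas.** Let p1 and p0 be the allele frequencies in steatotic and non-steatotic people.
- s·p1 + (1 − s)·p0 = 0.3
- odds(p1)/odds(p0) = steatosis OR
- Cases carry frequency p1, so apparent OR = odds(p1)/odds(0.3).
- z = (p1 − 0.3)/SE, with SE² = p1(1 − p1)/1600 + 0.3·0.7/4000
- Chance of reaching 5E-8 = Φ(z − 5.45)

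**4. Worked example (steatosis OR 2.0, s = 50%).** The solution is p0 = 0.228 and p1 = 0.372. The apparent OR is (0.372/0.628)/(0.3/0.7) = 1.38. SE = 0.0141, z = 5.1, and the chance is 36%. With the pooled-variance form of the test it is 40%.

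**5. Results** (pooled-variance form; the unpooled form differs by at most about 4 percentage points)

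| Steatosis OR | Steatotic controls | Apparent OR | Chance of reaching 5E-8 |
|---|---|---|---|
| 1.5 | 30% | 1.32 | 16% |
| 1.5 | 50% | 1.21 | 1% |
| 1.5 | 70% | 1.12 | under 0.1% |
| 2.0 | 30% | 1.59 | 98% |
| 2.0 | 50% | 1.38 | 40% |
| 2.0 | 70% | 1.21 | under 1% |
| 2.5 | 50% | 1.52 | 90% |
| 2.5 | 70% | 1.27 | 5% |

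At the suggestive threshold of 5E-6, the case with OR 2.0 and 50% steatotic controls passes with probability 73%.

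**6. Comparison with steatotic controls only.** Under the same simple model, both groups carry p1 and the apparent OR is 1.0. The control number becomes s × 2000, that is 600, 1000 or 1400. The table gives power at 5E-8 for a true progression effect at allele frequency 0.1.

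| Controls | True OR 2.0 | True OR 1.7 |
|---|---|---|
| 600 | 0.74 | 0.17 |
| 1000 | 0.95 | 0.44 |
| 1400 | 0.985 | 0.61 |
| all 2000 | 0.996 | 0.75 |

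**7. Precision of the estimate.** At allele frequency 0.3 and OR 1.0, the 95% half-width on the log scale is 1.96·√(1/(1600·0.21) + 1/(A·0.21)), where A is the number of control alleles. With A = 1200 it is 0.163 (OR 0.85 to 1.18). With A = 2800 it is 0.134 (0.87 to 1.14). With all 4000 it is 0.127 (0.88 to 1.13). For common variants the interval widens only modestly.

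**The case against.** **The formal aims are met.** A reader might infer that the study fails to answer its stated aim. The documents do not support that. Sections 2.1 and 5.1 ask about risk or presence of advanced MASLD, and a variant that raises that risk through steatosis is a valid hit there. The formal progression objective is somatic. This stands, and confines the point to the wording in 1.1 and 4.3.

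**Other germline analyses are planned.** A reader might also infer that the case-control comparison is the only germline analysis. It is not, because 4.3 and 5.2 plan tests on steatosis and fibrosis indicators. Setting those results side by side would often expose a steatosis locus. They remain separate tests of each trait, and do not show whether an effect on advanced disease persists given steatosis. Section 4.2 also mentions longitudinal follow-up of the donors, but no analysis is tied to it.

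**The size is uncertain.** Section 1.1 puts MASLD prevalence above 30% in the population, and these controls were selected for metabolic risk, so 30% is nearer a floor than a central value. This stands: at 70% or more the problem is small at 5E-8 unless the steatosis effect is strong.

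**The restricted contrast is not exact.** Conditioning on steatosis can bias the result if another factor causes both steatosis and progression. With an assumed factor present in 30% of people and ORs of 3 to 5 on both, a steatosis-only variant (OR 2.0 to 2.5) shows an OR of about 0.89 to 0.97 instead of 1.0. The bias is modest but should be acknowledged.

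**A restricted run could be left to an SAP.** That is fair for the analysis detail. The mismatch between the progression wording and the contrast is in the protocol itself.

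**Conclusion.** The point holds in a limited form. The primary contrast is sound for the objective and endpoint it serves, and should stay. The germline progression wording in 1.1 and 4.3 goes further than that contrast can show, and nothing else named in the protocol tests an effect on advanced disease among people with steatosis.

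The possible distortion ranges from large (apparent OR about 1.6 at 30% steatotic controls) to small (about 1.2 at 70%) for a steatosis OR of 2.0. These figures rest on an undocumented steatotic share, an assumed allele frequency and effect size, and all cases being steatotic. This is a matter of interpretation and labelling that is cheap to correct. It does not invalidate the main analysis.

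**What to change.** - Keep the comparison with all controls as primary.
- In 4.3 and 6.2, add a secondary REGENIE analysis of cases against Liver-BIBLE controls with Fibroscan-detected steatosis and no significant fibrosis. Evaluate the polygenic scores in the same contrast.
- Judge a progression claim by the effect estimate and interval in that contrast, not by genome-wide significance there, since the power loss would otherwise deny the label to genuine loci. State that conditioning on steatosis may bias estimates modestly.
- Otherwise, reword the germline claims in 1.1 and 4.3 as associated with risk or presence of advanced MASLD.

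**Cost.** Protocol wording and one further run on data already collected, with no new samples. The secondary contrast has about 600 to 1400 controls if 30-70% are steatotic, with the lower power shown above.

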#### 4.3 Sample analysis

The genetic analyses for this study will be conducted in close collaboration and under the supervision of Human Technopole.

As anticipated, the methodology envisaged for conducting this study involves whole-genome sequencing on DNA derived from peripheral blood (20x coverage) and pathological liver tissue (50x coverage) to characterize the genetic and somatic variants that influence disease progression.

The DNA will be isolated at the Foundation and shipped to the National Facility (NF) in batches of 3-4 plates at a time.

To identify associations between individual genetic variants and the burden of likely loss-of-function (LoF) variants at specific genetic loci, comparing participants with advanced MASLD to controls, analyses will be performed using a genome-wide regression model implemented in REGENIE, with additive genetic models accounting for age, sex, body mass index (BMI), and ancestry (BWI 1-10). To ensure the robustness of the results, the genome-wide significance threshold will be set at  $p < 5E-8$ . If the study is not powered to identify new significant associations, suggestive hits ( $p < 5E-6$ ) will be replicated in additional cohorts.

In addition to defining the risk of advanced MASLD compared to controls as the primary outcome, we will thoroughly examine the genetic contribution to various endophenotypes. These will include metabolic risk factors (such as insulin resistance indices), liver enzymes (AST, ALT, GGT), and indicators of liver damage (noninvasive predictors of steatosis, steatohepatitis, fibrosis, cirrhosis, and HCC). The results of these analyses will be crucial for improving risk stratification and identifying specific disease subphenotypes through the development of polygenic risk scores, which have previously proven effective in identifying subsets of patients at specific risk for liver or cardiovascular events. This approach will also aim to identify therapeutic targets with a high probability of clinical success.

As regards CHIP (Clonal Hematopoiesis of Indeterminate Potential) and somatic variants, their identification will take place through a semi-automated pipeline. CHIP assignment will be assessed in a panel of specific genes (including NADK, GNB1, CBL, KMT2D, RHEBL1, PPM1D, JMJD6, MFSD11, DNMT3A, SF3B1, ASXL1, NOL4L, GNAS, RUNX1, AF015262.1, RPL34P3, U2AF1, TET2, CUX1, SH2B2, BCOR, BCORL1, MCAM, TP53, TLMET23, SRSF2, NPM1P46, LINC01426, EZH2P1, F4, AT1PB2, ZNF316, ANAPC1, JAK2), while for somatic variants in hepatocytes, relevant scientific literature will be consulted. Variant identification will be performed using three callers: Mutect, Vardict, and Freebayes. The impact of inherited genetic variation on both CHIP risk and related phenotypes will also be assessed.

All unused material at the National Facility for Genomics will be returned and stored at the Fondazione IRCCS Ca Granda. Subject to the patient's specific consent for biobanking, these residues may be retained beyond the study's conclusion for future research purposes at the Foundation's POLI-MI Biobank.

## 5. ENDPOINT

### 5.1 Primary Endpoint

Identifying the association between germline variants and the presence of advanced MASLD in cases versus controls.

### 5.2 Secondary Endpoints

Other main endpoints of the study in question are:

- 1) Identification of somatic mutations in hepatocytes and hematopoietic cells in order to study their association with the development of HCC.
- 2) Use of PRS (existing in the literature and new) in predicting patterns of advanced MASLD among cases and controls
- 3) Analysis of the association between genetic variants and clinical and biological phenotypes of MASLD, considering metabolic markers, liver enzymes (AST, ALT, GGT) and non-invasive indicators of steatosis and fibrosis (Fibroscan)
- 4) Identification of functional variants (e.g. LoF) in genes involved in lipid metabolism, liver inflammation, oxidative stress associated with advanced MASLD.

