## FLOW CHART

	Screening	Intervention
Period	(-t1)	(t1)
Enlistment		
informed consent	x	
inclusion/exclusion criteria	x	
Administration of the intervention		
biological sample collection *		x
phenotypic data collection **		x

(\*) the biological sample has already been previously collected in the context of the SERENA, REASON or LIVER-BIBLE studies

(\*\*) These are data previously collected in the context of the SERENA, REASON or LIVER-BIBLE studies

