### 3.2 Inclusion criteria

Specific inclusion criteria for patients with advanced MASLD:

- Patients with advanced MASLD defined as liver fibrosis  $\geq 2$  and/or development of HCC;
- patients enrolled in the SERENA study and where applicable also in the REASON study;
- Liver biopsy for suspected non-alcoholic steatohepatitis (NASH) at the time of diagnosis;
- Cholecstectomies
- age [40-70 years]
- patients who have signed the informed consent

Specific inclusion criteria for control group:

Blood donors from the LIVER-BIBLE study aged between 40 and 70 years in the presence of overweight or obesity (Body mass index-BMI $>25\text{Kg/m}^2$ ) and at least two of the following risk factors:

- impaired fasting blood glucose or diabetes mellitus (blood glucose  $\geq 100 \text{ mg/dl}$ )

- dyslipidemia (triglycerides $\geq$ 150mg/dl, HDL $<$ 45/55 in M/F)
- arterial hypertension

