### 3.3 Exclusion criteria

Specific exclusion criteria for patients with advanced MASLD:

- Positivity for chronic viral hepatitis (HCV-RNA and/or HBsAg);
- Positivity for other liver diseases such as autoimmune and viral hepatitis (hepatitis B and C), hereditary hemochromatosis, alpha-1-antitrypsin deficiency, Wilson's disease.

Specific exclusion criteria for the control group:

Subjects suffering from chronic degenerative diseases will be excluded, with the exception of well-controlled hypertension and type 2 diabetes mellitus not requiring pharmacological therapy (as is already common practice for eligibility to donate blood) and donors aged  $>$  65 and  $<$  40.

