## **4. PROCEDURES RELATING TO THE STUDY**

### **4.1 Patient recruitment**

Patient enrollment will take place at the outpatient clinics of the Transfusion Medicine Unit of the Fondazione IRCCS Ca' Granda Ospedale Maggiore Policlinico during routinely scheduled visits.

If obtaining consent for the clinical study is not compatible with the conduct of the study, consent will be obtained remotely via telephone, as described in chapter 9.2.3.

In all other cases, the informed consent process will be managed in person.

Patients who enroll in the DETECTIVE study will not undergo any additional procedures, but will consent to the use of data and biological samples previously collected in the SERENA, REASON, and Liver-Bible studies.

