- Biomarkers of Liver Injury and Function: Liver enzymes such as alanine aminotransferase (ALT), aspartate aminotransferase (AST), gamma-glutamyl transpeptidase (GGT), and alkaline phosphatase (ALP) levels, indicators of hepatocellular injury or cholestasis.
- Liver synthetic function: Bilirubin, albumin, prothrombin time/INR, which reflect the liver's synthetic capacity.
- Non-invasive biomarkers of liver damage: data from tools such as Fibroscan or predictive score calculations (e.g., FIB-4, NAFLD Fibrosis Score) to assess the presence and degree of steatosis, steatohepatitis (NASH), fibrosis, and cirrhosis.
- Metabolic Risk Factors: such as data on glucose, lipids (total cholesterol, HDL, LDL, triglycerides), insulin, HbA1c and indices of insulin resistance (e.g. HOMA-IR), which are essential for outlining the metabolic profile underlying MASLD.
- Inflammatory Biomarkers: Such as C-reactive protein (CRP) and ferritin, useful for assessing systemic and/or hepatic inflammatory status.
- Hepatocellular Carcinoma (HCC) Data: For patients who have developed HCC, specific information on diagnosis, staging, oncological treatments and follow-up is collected, essential for studying clonal evolution.

- For Metabolic Controls, aimed at providing an extremely in-depth baseline characterization of their general health and metabolic risk profile, in the absence of advanced MASLD, to serve as a robust comparison:
  - Detailed Anthropometric Assessment: Height, weight, waist circumference, BMI, for a precise quantification of adiposity.
  - Detailed Medical History: Lifestyle, eating habits (diet), complete medical history, with particular attention to the presence of metabolic risk factors (hyperglycemia, hypertension, dyslipidemia, increased adiposity) which are inclusion criteria.

- Complete Blood Count: Evaluation of the cellular components of the blood.
- Coagulation Parameters: Includes factors such as FVIII, VWF, protein C (PC) and D-dimer.
- Standard Clinical Biochemistry: Includes assessments of general liver and renal function, as well as inflammatory biomarkers.
- Complete Metabolic Profiles: Glucose, lipids (total cholesterol, HDL, LDL, triglycerides), insulin and HbA1c, to quantify metabolic risk factors.
- Liver Biomarkers: Although not targeted to progression of advanced MASLD, baseline biomarkers of liver function are included to ensure the absence of significant non-MASLD liver disease.

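### The blood half of secondary endpoint 1 speaks of development of HCC, but sets no condition on whether the stored blood predates HCC diagnosis or cancer treatment

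*Protocol*

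**What the plan says.** - **Endpoint.** Section 5.2, item 1: "Identification of somatic mutations in hepatocytes and hematopoietic cells in order to study their association with the development of HCC". By contrast, the primary endpoint in section 5.1 concerns the presence of advanced MASLD.
- **Samples.** The flow chart notes that "the biological sample has already been previously collected in the context of the SERENA, REASON or LIVER-BIBLE studies". Section 4.1 adds no procedure: participants "will consent to the use of data and biological samples previously collected in the SERENA, REASON, and Liver-Bible studies". Section 3.1 dates the approval of SERENA, the source of the 800 patient blood samples, to 2017. The timeline puts enrolment between September and December 2025.
- **Case entry.** Section 3.2 accepts fibrosis of grade 2 or more "and/or development of HCC". The exclusions for cases in section 3.3 cover viral and other liver diseases. Earlier HCC and earlier cancer treatment are not among them.
- **CHIP method.** Section 4.3 says "CHIP assignment will be assessed in a panel of specific genes" and names three variant callers. It has no rule on sample timing. The covariates given there, "additive genetic models accounting for age, sex, body mass index (BMI), and ancestry", belong to the germline model.
- **HCC data.** For patients with HCC, section 4.2 states that "specific information on diagnosis, staging, oncological treatments and follow-up is collected, essential for studying clonal evolution". No section links these data to the date of the blood draw or to the CHIP analysis.

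**The concern.** A germline variant is fixed, so the date of the draw does not matter for the primary endpoint. A blood clone is acquired and changes over time. The protocol treats it that way itself when it writes of accumulating somatic variants (section 1.1) and of clonal evolution (section 4.2).

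Under the entry criteria, three HCC patients would count alike in a CHIP analysis: one bled before the tumour appeared, one bled at diagnosis, and one bled after cancer treatment. Only the first can speak to whether CHIP precedes HCC. In the third, the clone may follow from the disease or its treatment.

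What is at stake is the conclusion drawn. Section 1.1 raises the possibility that CHIP promotes HCC, and the first secondary objective in section 2.2 concerns somatic variants involved in progression. An excess of CHIP in post-treatment blood would look like support for both, even if CHIP had no effect on HCC.

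**Working it through.** The protocol gives no sample size, power or effect size for the CHIP–HCC endpoint, so there is no figure to reproduce. The check has two parts.

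**1. Is the time order secured anywhere?**

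| Where it could be secured | What is found |
|---|---|
| Sample collection (flow chart, 4.1, 4.2) | Stored blood, no condition on draw date |
| Inclusion (3.2) | Existing HCC qualifies a case |
| Exclusion (3.3) | Prior HCC or cancer treatment not listed |
| CHIP method (4.3) | Genes and callers, no timing rule |
| HCC data (4.2) | Diagnosis and treatment collected, not linked to the draw |
| Prospective follow-up (4.2) | Described for the Liver-BIBLE controls, not as follow-up of patients for new HCC |

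The order of blood draw and HCC is left open throughout.

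**2. How large could a treatment-driven artefact be?** Every input here is an assumption, because the protocol supplies none.

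- CHIP prevalence without HCC, and in HCC before treatment: p0 = 0.10, so there is no true effect.
- CHIP prevalence after cancer treatment: pT = 0.20.
- Share of HCC patients bled after treatment: f = 0.25, 0.50 or 0.75.

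Observed prevalence in HCC: p1 = (1 − f) × 0.10 + f × 0.20.

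False odds ratio: [p1/(1 − p1)] / [0.10/0.90].

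| f | p1 | False odds ratio |
|---|---|---|
| 0.25 | 0.125 | (0.125/0.875)/(0.10/0.90) = 1.29 |
| 0.50 | 0.150 | (0.150/0.850)/(0.10/0.90) = 1.59 |
| 0.75 | 0.175 | (0.175/0.825)/(0.10/0.90) = 1.91 |

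A wider grid took p0 from 5% to 15%, treatment raising the odds of detectable CHIP by 1.5 to 3 times, and f from 25% to 100%. The false odds ratio then runs from 1.12 to 3.0.

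A middle case in that grid is p0 = 10%, odds doubled and f = 50%:

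- Treated odds are 2 × 0.10/0.90 = 0.222, so pT = 0.182.
- p1 = 0.5 × 0.182 + 0.5 × 0.10 = 0.141.
- The false odds ratio is 1.48.

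With 50, 100 or 200 HCC cases among the 800 patients (again assumed), that middle case would be declared significant at two-sided 0.05 with probability 0.18, 0.26 or 0.37.

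If no HCC blood was drawn after treatment, f = 0 and this part of the odds ratio returns to 1. Removing post-treatment samples does the same. It does not settle the order of clone and tumour in samples taken at or after diagnosis.

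**The case against.** The best case for the plan has five parts.

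- **The endpoint claims only association, in a study that section 6.1 calls descriptive.** This is fair, and it is why rewording goes a long way. The endpoint still names development, and the objective names progression.
- **Development may be loose wording for disease status.** Section 2.1 defines advanced disease by hepatocellular carcinoma, and section 3.2 gives the same definition as development of HCC. Incident HCC is therefore not the only possible reading. If status is meant, the wording should say so.
- **Sample selection and covariates can sit in a statistical analysis plan.** That holds for model detail. The endpoint's claim, and which stored sample counts as exposure, are set in the protocol.
- **A reader might infer that cause and consequence cannot be separated at all.** The documents do not support that. Section 4.2 collects HCC diagnosis and treatment data, so with draw dates from the parent studies some separation may be possible. The gap is in the plan, not necessarily in the data.
- **A reader might also infer that post-treatment blood has in fact been used.** No section shows this. When SERENA drew blood is not described here, and the effect of cancer treatment on CHIP is an assumption.

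Making pre-diagnostic blood the main analysis would also go too far. The number of HCC patients is not stated, and no follow-up of patients for new HCC is described. Such an analysis might have almost no cases.

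**Conclusion.** The point holds for the blood half of secondary endpoint 1. As written, the plan can support a statement that CHIP and HCC occur together, but not one about the development of HCC. Samples drawn after treatment could inflate the association in the hypothesised direction.

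The size cannot be determined from the protocol. The range of about 1.3 to 1.9 rests wholly on the assumed prevalences and the assumed share of post-treatment draws. The artefact is zero if no HCC blood was drawn after treatment, which the protocol neither states nor requires. The conclusion about time order does not depend on these figures.

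The primary germline endpoint is not affected. Mutations in liver tissue raise a different question, which this point does not cover. The change is worth making before the CHIP results are seen, so that the choice of samples is not made afterwards.

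**What to change.** 1. In section 5.2, word the CHIP part of endpoint 1 as association with the presence of HCC.
2. In section 4.3, classify each HCC patient's blood as drawn before diagnosis, after diagnosis but before oncological treatment, or after treatment. Use the HCC data listed in section 4.2 and the draw dates from the parent studies. That those dates are held is an assumption to confirm.
3. Report the CHIP–HCC association with post-treatment samples excluded. Compare with advanced-MASLD patients who have no recorded HCC, and use age at blood draw as the age covariate.
4. Keep the word *development* for an analysis of the pre-diagnostic subset, and run it only if there are enough such samples.

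The cost is protocol wording, the retrieval of draw dates, fewer HCC cases and a wider interval in the restricted analysis. No new samples are needed, and every blood sample stays in the germline primary analysis.
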